7.2.3. Dose Progression through Study Parts

Safety will be the primary criteria for the dose escalation or de-escalation of both olaratumab monotherapy and the combination regimens. No dose escalation can occur without prior discussion and agreement between the investigators and the Lilly CRP/CRS/Lilly study team; the decision will be documented in writing. Sites will be notified of this decision in writing.

Based on the ongoing safety reviews, modifications to the dose-escalation strategy or other design elements may be made via protocol amendment to ensure patient safety.

Part B will be initiated after acceptable safety results from Part A, including a minimum of 6 evaluable patients, and the PK profile from Part A monotherapy. Part B will be complete when at least 10 patients (regardless of assigned chemotherapy arm) are evaluable for safety of olaratumab 20 mg/kg monotherapy.

Part C will open for enrollment after a complete safety review of the first 10 patients (regardless of chemotherapy arm) to complete Part B monotherapy (olaratumab 20 mg/kg). This safety review will be performed by the Lilly CRP/CRS/Lilly study team and investigators and documented in writing. Sites will be notified of this decision in writing.

7.2.3.1. Dose-Limiting Toxicity Determination and Maximum Tolerated Dose Definition

A DLT is defined as an adverse event (AE) during the first 21 days that is possibly related to the study drug and fulfills any one of the following criterion using the National Cancer Institute's (NCI) Common Terminology Criteria for Adverse Events (CTCAE) v 4.0:

- CTCAE Grade ≥ 3 nonhematologic toxicity. Exceptions will be made for:
 - Grade 3 febrile neutropenia without complications,
 - Grade 3 events of nausea, vomiting, diarrhea, transient electrolyte abnormalities, and constipation that can be controlled with optimal medical management within 48 hours, and
 - transient Grade 3 elevations of ALT and/or AST lasting fewer than 8 days, without evidence of other hepatic injury may not be considered a DLT if agreed by the study investigator and Lilly CRP/CRS.
- Grade 4 neutropenia that lasts longer than 2 weeks
- Grade ≥ 3 thrombocytopenia complicated by hemorrhage
- Any hematologic toxicity that causes a cycle delay of > 14 days
- Any other significant toxicity deemed by the primary investigator and Lilly clinical research personnel to be dose limiting (for example, any toxicity that is possibly related to the study medication that requires the withdrawal of the patient from the study during Cycle 1)

7.2.3.2. Dose-Escalation Method

Part B will be initiated after the following criteria have been met:

- Acceptable safety results, which must include a minimum of 6 evaluable patients, and the PK profile from Part A monotherapy
- At least one of the 15 mg/kg combination arms has met the following DLT criteria: less than one third (that is, approximately 33.3% [minimum of 3 patients]) DLT rate. Only the combination arms in Part A that have met these criteria may be studied in Parts B and C.

In Part A, if the DLT rate is $> 1/3$ (that is, greater than 4 out of 12 patients) during Cycle 1 monotherapy, then the dose of olaratumab will be reduced to 10 mg/kg. In Part B, if the DLT rate is $> 1/3$ during Cycle 1 monotherapy, then the dose of olaratumab will be reduced to

15 mg/kg. In Part C, if the DLT rate is >1/3 during Cycle 1 combination therapy, then the dose of olaratumab will be reduced to 15 mg/kg.

If the DLT rate is >1/3 in the first cycle (Parts A and B Cycle 2, or Part C Cycle 1) of any of the chemotherapy arms, then appropriate dose de-escalation ([Table JGDN.7.3](#)) of olaratumab for that combination will occur.

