Length of Study: Planned first patient visit: 11 February 2016 Planned last patient visit: 05 June 2019	
Objectives: The primary objective of this study is to determine a recommended dose of olaratumab in combination with at least one of the studied chemotherapy regimens in pediatric patients based on any dose-limiting toxicities (DLTs) as well as olaratumab serum exposure-matching between the adult and pediatric populations. The secondary objectives of this study are: 
to investigate the pharmacokinetics (PK) of olaratumab as monotherapy and in combination with either doxorubicin, vincristine/irinotecan, or high-dose ifosfamide in pediatric patients;to assess the possible development of antibodies against olaratumab (immunogenicity) in pediatric patients; andto document any antitumor activity (including progression-free survival and objective response rate [ORR]) observed with olaratumab in combination with either doxorubicin, vincristine/irinotecan, or high-dose ifosfamide in pediatric patients. The exploratory objective of this study is: 
to identify exploratory biomarkers associated with tumor response and/or safety. Study Design: Study JGDN is a multicenter, dose-escalation, open-label Phase 1 pediatric safety clinical trial with 3 distinct components, Part A, Part B, and Part C. Part A will consist of at least 12 evaluable pediatric patients. These patients will be treated for 1 cycle (21 days) of olaratumab monotherapy at 15 mg/kg on Day 1 and Day 8 (adult dose for which efficacy was observed in Study I5B-IE-JGDG). If the patient does not experience a DLT in the first cycle of monotherapy, or meet any other criteria for discontinuation, the patient will then receive olaratumab (15 mg/kg) plus one of 3 standard chemotherapy regimens (doxorubicin or vincristine/irinotecan or high-dose ifosfamide per investigator discretion). Treatment will continue until disease progression or other discontinuation criteria are met. Part B will be initiated after the following criteria have been met: 
Acceptable safety results, which must include a minimum of 6 evaluable patients, and the PK profile from Part A monotherapy.At least one of the 15 mg/kg combination arms has met the following DLT criteria: less than one-third (that is, approximately 33.3% [minimum of 3 patients]) DLT rate. Only the combination arms in Part A that have met these criteria may be studied in Parts B and C.	

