6.2. Summary of Study Design

[figure not shown]
Study JGDN is a multicenter, dose-escalation, open-label Phase 1 pediatric safety clinical trial with 3 distinct components, Part A, Part B, and Part C.

Part A will consist of at least 12 evaluable pediatric patients. Given the expected diversity of age and body weight in the study population, this sample size is expected to provide the necessary amount of PK information in order to characterize the disposition of olaratumab in the pediatric population.

Patients will be treated for 1 cycle (21 days) of olaratumab monotherapy at 15 mg/kg on Day 1 and Day 8 (adult dose for which efficacy was observed in Study JGDG). If the patient does not experience a DLT in the first cycle of monotherapy, or meet any other criteria for discontinuation, the patient will then receive olaratumab (15 mg/kg) plus one of 3 standard chemotherapy regimens (doxorubicin or vincristine/irinotecan or high-dose ifosfamide per investigator discretion). Treatment will continue until disease progression or other discontinuation criteria are met.

During Cycle 1 monotherapy, if the DLT rate is >1/3 (that is, greater than 4 out of 12 patients), then the dose of olaratumab will be reduced to 10 mg/kg. If the DLT rate is >1/3 in the first cycle (Cycle 2) of any of the combination therapy arms, then appropriate dose de-escalation of olaratumab for that combination will occur. Another cohort with at least 3 patients will be studied for that combination with olaratumab at 10 mg/kg.

Part A of the study design is illustrated in [Figure JGDN.6.1](#).

Part A**Figure JGDN.6.1. Illustration of Part A of the study design.**

Part B will be initiated after the following criteria have been met:

- Acceptable safety results, which must include a minimum of 6 evaluable patients, and the PK profile from Part A monotherapy.
- At least one of the 15 mg/kg combination arms has met the following DLT criteria: less than one-third (that is, approximately ~33.3% [minimum of 3 patients]) DLT rate. Only the combination arms in Part A that have met these criteria may be studied in Part B.

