Part B patients will be treated for 1 cycle (21 days) of olaratumab monotherapy at 20 mg/kg on Day 1 and Day 8 then receive olaratumab (20 mg/kg) plus one of 3 standard chemotherapy regimens described in Part A. Part B will be complete when at least 10 patients (regardless of assigned chemotherapy arm) are evaluable for safety of olaratumab 20 mg/kg monotherapy. Treatment will continue until disease progression or other discontinuation criteria are met.

[figure not shown]
In Part B, if a patient has a DLT during the Cycle 1 monotherapy, the subsequent olaratumab dose will be reduced to 15 mg/kg, and the patient will receive combination therapy in Cycle 2.

During Cycle 1 monotherapy, if the DLT rate is >1/3 (that is, greater than 4 out of 12 patients), then the dose of olaratumab will be reduced to 15 mg/kg for patients subsequently enrolled. If

the DLT rate is $>1/3$ in any of combination therapy arms, then appropriate dose de-escalation of olaratumab for that combination will occur.

Part B is illustrated in [Figure JGDN.6.2](#).

Part B

[figure not shown]
Abbreviations: D = day; DLT = dose-limiting toxicity; N = number of patients; n = number of cycles.

Figure JGDN.6.2. Illustration of Part B of the study design.

Part C will receive olaratumab (20 mg/kg) in combination with any of the 3 chemotherapy regimens from Cycle 1 onwards (ie. no olaratumab monotherapy in Cycle 1). Treatment will continue until disease progression or other discontinuation criteria are met.

Part C is illustrated in [Figure JGDN.6.3](#).

Part C

Abbreviations: DLT = dose-limiting toxicity; n = number of cycles.

Figure JGDN.6.3. Illustration of Part C of the study design.

Parts B and C together will enroll up to 45 patients (15 per chemotherapy arm).

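### The gate for Part A combination arms is blurred at exactly one third, Protocol 6.2 keeps a 12-patient count for a Part B reviewed at 10, and the SAP still sizes Part B at 12 or more

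*Protocol*

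**What the plan says.** **Gate into Parts B and C.** At least one 15 mg/kg combination arm must meet the criterion worded in the Protocol synopsis as "less than one-third (that is, approximately 33.3% [minimum of 3 patients]) DLT rate", in 6.2 as "less than one-third (that is, approximately ~33.3% [minimum of 3 patients]) DLT rate", and in 7.2.3.2 as "less than one third (that is, approximately 33.3% [minimum of 3 patients]) DLT rate". SAP 5.1 repeats it in its text and in the Part B initiation column of Figure JGDN.2. Protocol 7.2.3.2 adds: "Only the combination arms in Part A that have met these criteria may be studied in Parts B and C".

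**De-escalation of a combination.** Protocol 7.2.3.2 uses a strict inequality: "If the DLT rate is >1/3 in the first cycle (Parts A and B Cycle 2, or Part C Cycle 1") of any chemotherapy arm, olaratumab is reduced for that combination.

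**Part B monotherapy rule.** Protocol 6.2 says "During Cycle 1 monotherapy, if the DLT rate is >1/3 (that is, greater than 4 out of 12 patients"), the dose falls to 15 mg/kg for later enrolments. The same words appear in its Part A paragraph. Section 7.2.3.2 gives Part B the rate alone, with no count.

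**Part B size.** Protocol 6.2: "Part B will be complete when at least 10 patients (regardless of assigned chemotherapy arm) are evaluable" for safety of 20 mg/kg monotherapy. Protocol 7.2.3: "Part C will open for enrollment after a complete safety review of the first 10 patients" to complete Part B monotherapy. SAP version 3 (26 November 2018), whose revision history says it was updated for Part C, still gives Part B at least 12 evaluable patients in 5.1 and about 12 in the 20 mg/kg entry of Figure JGDN.2. Protocol amendment (b) is dated 14 February 2018.

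**The concern.** These are the printed thresholds for giving or reducing olaratumab 20 mg/kg in children, and DLT is one of the two components of the primary endpoint (Protocol 6.2.1).

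The gate explains a strict inequality by quoting the boundary value. One reader will hold an arm with 1 DLT in 3 patients at 15 mg/kg; another will call 1 of 3 approximately 33.3% and let it through. Three is the protocol's own minimum arm size, so the case is not remote.

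The Part B count belongs to a cohort of 12, yet the review that opens Part C uses 10. The SAP gives a third party checking the conduct of Part B a different cohort size from the protocol.

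**Working it through.** **Inputs.** Gate: rate below 1/3, minimum 3 patients (Protocol 7.2.3.2). De-escalation: rate above 1/3 (same section). Printed Part B count: more than 4 of 12 (Protocol 6.2). Part B review size: 10 (Protocol 6.2 and 7.2.3). The documents give no pediatric DLT rate, so true rates p of 10%, 20%, 1/3 and 40% are assumed, with independent patients and X ~ Binomial(n, p).

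**Step 1: the plan's own figure.** 12 × 1/3 = 4, so above 1/3 means 5 or more of 12, that is, more than 4. The printed count is correct for 12 patients, and so for Part A.

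**Step 2: the same rate at other sizes.**

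| Evaluable n | Advance (below 1/3) | Exactly 1/3 | De-escalate (above 1/3) |
|---|---|---|---|
| 3 | 0 | 1 | 2 or more |
| 4 or 5 | 0–1 | not possible | 2 or more |
| 6 | 0–1 | 2 | 3 or more |
| 9 | 0–2 | 3 | 4 or more |
| 10 or 11 | 0–3 | not possible | 4 or more |
| 12 | 0–3 | 4 | 5 or more |

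At 10 patients, 3/10 = 0.300 and 4/10 = 0.400, so the rule triggers at 4. The boundary result occurs only when n is a multiple of 3.

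**Step 3: how often the gate boundary arises, given the arm size.**

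| | p = 10% | 20% | 1/3 | 40% |
|---|---|---|---|---|
| P(X = 1), n = 3 | 0.243 | 0.384 | 0.444 | 0.432 |
| P(X = 2), n = 6 | 0.098 | 0.246 | 0.329 | 0.311 |
| P(advance), n = 3, strict (0 DLTs) | 0.729 | 0.512 | 0.296 | 0.216 |
| P(advance), n = 3, if 1/3 is let through | 0.972 | 0.896 | 0.741 | 0.648 |

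For example, P(X = 1) at n = 3 and p = 0.2 is 3 × 0.2 × 0.8² = 0.384.

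**Step 4: Part B at 10 patients.** The rate triggers at 4 or more. A bare cut-off of more than 4, with its denominator dropped, triggers at 5 or more. They differ only at exactly 4.

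| | p = 10% | 20% | 1/3 | 40% |
|---|---|---|---|---|
| P(X ≥ 4) | 0.013 | 0.121 | 0.441 | 0.618 |
| P(X ≥ 5) | 0.002 | 0.033 | 0.213 | 0.367 |
| P(X = 4), the difference | 0.011 | 0.088 | 0.228 | 0.251 |

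**The case against.** The strongest reply is that nothing here is undefined. Below 1/3 advances, above 1/3 de-escalates, and exactly 1/3 stays where it is. A hold zone between two thresholds is coherent. That stands, and it is the right reading of the strict words; what remains is a gloss that invites the other one.

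For Part B, the rule is a rate that works at any n, and 7.2.3.2 states it for Part B with no count. SAP 5.1 offers the 12-patient count only as an example. At least 10 also permits 12, where the count is right. This stands too: the error is confined to the parenthesis in Protocol 6.2, which is worded as the meaning of the rule and not as an illustration.

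Two stronger inferences are tempting, and neither is supported:

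- A reader might infer that SAP Figure JGDN.2 contradicts its own gate, because its branches are only acceptable or above 1/3. The acceptable branch leads to continued dosing at 15 mg/kg, and a separate column carries the gate for Part B. Acceptable need not mean advance.
- A reader might infer that the figure applies more than 4 of 12 throughout Part B. As printed, the count appears only in the 10 mg/kg row, whose own size is about 12, so it is correct there. The 20 mg/kg row gives the rate alone.

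Finally, the boundary may be rare. Twelve Part A patients over three arms is 12/3 = 4 each. About 20 per arm overall less 15 in Parts B and C is 5. Exactly 1/3 cannot occur at either size. So the step 3 probabilities hold only for an arm of 3 or 6.

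**Conclusion.** The point holds in three limited parts.

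1. The gate wording is ambiguous at exactly 1/3. In an arm of 3 the boundary has probability 24% to 44% over assumed rates of 10% to 40%; in an arm of 6, 10% to 33%; at 4 or 5, zero.
2. The Part B parenthesis in Protocol 6.2 is stale. If the >1/3 rate is applied, as the text directs, no decision changes. Keeping more than 4 while dropping the 12 would change the decision with probability 1% to 25%, but no document instructs that reading, so this is the cost of a slip and not the operating behavior of the plan.
3. The SAP's Part B size conflicts with the protocol's. The analyses are descriptive (SAP 5.2), so no estimate or test depends on the 12.

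Protocol 7.2.3 also requires agreement between investigators and sponsor, documented in writing, before any escalation. That limits the harm, but the people agreeing need one readable threshold. This should be corrected; it does not invalidate the design. The probabilities rest on assumed DLT rates and independent patients; the counts in step 2 rest on neither.

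**What to change.** **(a) Gate.** In the Protocol synopsis, 6.2 and 7.2.3.2, and in SAP 5.1 including the gate in Figure JGDN.2, delete the gloss that equates the criterion with 33.3%. Keep less than one third with a minimum of 3 evaluable patients, and add that an arm at exactly 1/3 stays at 15 mg/kg and does not advance. Counts to advance: 0 of 3, at most 1 of 4–6, at most 2 of 7–9, at most 3 of 10–12.

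**(b) Part B rule.** In Protocol 6.2 and the SAP 5.1 text, replace the count with: more than 1/3 of evaluable patients (for example, 4 or more of 10, or 5 or more of 12). Do not tie the assessment to a single look at 10. Protocol 7.2.3 provides for ongoing safety reviews, and 4 DLTs in the first 8 patients already guarantee at least 4/10. That has probability 26% at a true rate of 1/3 and 41% at 40%, so waiting for 10 could delay a reduction. Leave the 10 mg/kg row of Figure JGDN.2 alone.

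**(c) Part B size.** Change SAP 5.1 and the 20 mg/kg entry of Figure JGDN.2 to at least 10 evaluable patients.

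**Cost.** Wording in both documents; no extra patients are required. The downside of stating the strict gate openly is that one DLT in a 3-patient arm bars that combination from 20 mg/kg unless more patients are evaluated. A 3-patient arm fails to advance with probability 1 − 0.729 = 27% at a true rate of 10% and 1 − 0.512 = 49% at 20%. For a 4-patient arm the figures are 5% and 18%. Protocol 7.3 already allows more than 3 patients per combination in Part A when eligible patients consent concurrently and the sponsor approves.

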7.2.4. Dose Adjustments and Delays

In the event that a patient experiences a DLT or a DLT-equivalent (a DLT occurring in Cycle 3 or later of Parts A and B or Cycle 2 or later of Part C), treatment will be interrupted. Dosing can be resumed after resolution of the toxicity to baseline levels at the next lower dose level ([Table JGDN.7.3](#)) already deemed safe upon discussion with the Lilly CRP/CRS. For Grade 3/4 toxicities that are not dose-limiting, see Section [7.2.4.1.2](#) for hematologic toxicities and Section [7.2.4.1.3](#) for nonhematologic toxicities.

Table JGDN.7.3. Olaratumab Dose Levels and Adjustments for Olaratumab-related Toxicities

Dose at Enrollment	Dose Reduction		
	First	Second	Third
Dose level 3	20 mg/kg	15 mg/kg	10 mg/kg
Dose level 2	15 mg/kg	10 mg/kg	discontinue olaratumab
Dose level 1	10 mg/kg	discontinue olaratumab	

In the event of alteration of olaratumab therapy due to an olaratumab-related toxicity, chemotherapy need not be altered, and the planned chemotherapy schedule should be maintained. In the event that olaratumab treatment is discontinued for reason of toxicity, the patient should be discontinued from the study.

Similarly, olaratumab therapy should not be altered for chemotherapy-related toxicity, even if the chemotherapy dose is modified. In the event that chemotherapy is discontinued for reason of toxicity, the patient should be discontinued from the study.

To begin dosing at each cycle, the following criteria must be fulfilled:

- ANC $\geq 750/\text{mm}^3$
- Platelets $\geq 75,000/\text{mm}^3$
- Hemoglobin $\geq 8 \text{ g/dL}$
- Total bilirubin $\leq 1.5 \times \text{ULN}$
- AST and ALT $\leq 3.0 \times \text{ULN}$, or $\leq 5 \times \text{ULN}$ if the transaminase elevation is due to liver metastases
- Any nonhematologic toxicity that are NCI-CTCAE, v4.0 Grade <2 or equivalent severity to baseline

Treatment may be delayed for up to 14 days to allow a patient sufficient time for recovery from study drug-related toxicity.

The following information (in this section and the following subsections) pertains to dose modifications and delays for and management of AEs of concern, which may or may not be associated with olaratumab therapy, including the following:

- IRR (see Section [7.2.4.1.1](#))
- Hematologic toxicity (see Section [7.2.4.1.2](#))
- Nonhematologic toxicity (see Section [7.2.4.1.3](#))

The following information (in this section and the following subsections) pertains to dose modifications and delays for and management of AEs of concern, which may or may not be associated with doxorubicin therapy, including the following:

- Hematologic toxicity (see Section [7.2.4.2.1](#))
- Cardiovascular toxicity (see Section [7.2.4.2.2](#))
- Hepatic impairment (see Section [7.2.4.2.3](#))

The following information (in this section and the following subsections) pertains to dose modifications and delays for and management of AEs of concern, which may or may not be associated with vincristine therapy, including the following:

- Hematologic toxicity (see Section [7.2.4.3.1](#))
- Nonhematologic toxicity (see Section [7.2.4.3.2](#))

The following information (in this section and the following subsections) pertains to dose modifications and delays for and management of AEs of concern, which may or may not be associated with irinotecan therapy, including the following:

- Hematologic toxicity (see Section [7.2.4.4.1](#))
- Diarrhea and cholinergic reactions (see Section [7.2.4.4.2](#))

The following information (in this section and the following subsections) pertains to dose modifications and delays for and management of AEs of concern, which may or may not be associated with ifosfamide therapy, including the following:

- Urotoxic effects (see Section [7.2.4.5.1](#))
- Proximal tubular damage (see Section [7.2.4.5.2](#))
- Central nervous system (see Section [7.2.4.5.3](#))
- Other Toxicities (see Section [7.2.4.5.4](#))

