Upon documentation of pregnancy, the patient must be removed from the study and treatment with study drug(s) must be stopped immediately.

For all enrolled patients, study site personnel will record the occurrence and nature of each patient's preexisting condition(s), including clinically significant signs and symptoms of the disease under treatment in the study. While the patient is on study, site personnel will record any change in these preexisting condition(s) and the occurrence and nature of any AEs. In addition, all AEs related to protocol procedures are reported to Lilly or designee.

If a patient's dosage is reduced or treatment is discontinued as a result of an AE, study site personnel must clearly report to Lilly or its designee via eCRF the circumstances and data leading to any such dosage reduction or discontinuation of treatment.

Investigators will be instructed to report to Lilly or its designee their assessment of the potential relatedness of each AE to protocol procedure or study drug via eCRF.

The investigator decides whether he or she interprets the observed AEs as either related to disease, study medication, study procedure, or other concomitant treatment or pathologies. To assess the relationship of the AE to the study drug, the following terminologies are defined:

- **Related:** a direct cause and effect relationship between the study treatment and the AE is likely.

- **Possibly related:** a cause and effect relationship between the study treatment and the AE has not been demonstrated at this time and is not probable, but is also not impossible.
- **Unrelated:** without question, the AE is definitely not associated with the study treatment.

As per Lilly's standard operating procedures, all "related" and "possibly related" AEs and SAEs will be defined as related to study drug.

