#### Dose Limiting Toxicity (DLT)

Dose-limiting toxicity is defined as an AE during Cycle 1 (Cycle 2 for combination treatment) for a patient enrolled in Part A and Part B that is possibly related to the study drug and fulfills any one of the following criterion using the National Cancer Institute's Common Terminology Criteria for Adverse Events (NCI-CTCAE) Version 4.0:

- CTCAE Grade >3 nonhematologic toxicity. Exceptions will be made for:
  - Grade 3 febrile neutropenia without complications,
  - Grade 3 events of nausea, vomiting, diarrhea, transient electrolyte abnormalities, and constipation that can be controlled with optimal medical management within 48 hours, and
  - transient Grade 3 elevations of alanine transaminase (ALT) and/or aspartate aminotransferase (AST) lasting fewer than 8 days,
  - without evidence of other hepatic injury may not be considered a DLT if
  - agreed by the study investigator and Lilly CRP/CRS.
- Grade 4 neutropenia that lasts longer than 2 weeks
- Grade  $\geq 3$  thrombocytopenia complicated by hemorrhage
- Any hematologic toxicity that causes a cycle delay of >14 days
- Any other significant toxicity deemed by the primary investigator and Lilly clinical research personnel to be dose limiting (for example, any toxicity that is possibly related to the study medication that requires the withdrawal of the patient from the study during Cycle 1)

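### Two dosing rules cover the same olaratumab-related Grade 4 nonhematologic toxicity with no stated precedence, and Section 6.2 keeps on olaratumab Part B children whom Section 7.2.4.1.1 takes off it

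*Protocol*

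**What the plan says.** **The DLT rule.** Under Protocol 7.2.4, a DLT or DLT-equivalent interrupts treatment. After that, "Dosing can be resumed after resolution of the toxicity to baseline levels at the next lower dose level", provided the lower level has been judged safe and the sponsor's physician has been consulted. Nothing is said about a second event. A DLT-equivalent is "a DLT occurring in Cycle 3 or later of Parts A and B or Cycle 2 or later of Part C".

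**The pointers to the toxicity tables.** The same paragraph continues: "For Grade 3/4 toxicities that are not dose-limiting", the reader should go to 7.2.4.1.2 (hematologic) or 7.2.4.1.3 (nonhematologic). Later in 7.2.4, a list of adverse events of concern names 7.2.4.1.3 again, this time without limiting it to events that are not dose-limiting.

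**The Grade 4 row.** Section 7.2.4.1.3 and Table JGDN.7.5 cover olaratumab-related nonhematologic toxicity other than infusion reactions. The Grade 4 row speaks of any patient with such an event. It asks that permanent discontinuation be considered, allows resumption at a reduced dose only after consulting the sponsor's physician, and requires olaratumab to stop if Grade 4 recurs.

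**Part B and infusion reactions.** Protocol 6.2 says that a Part B patient with a DLT in the monotherapy cycle goes down to 15 mg/kg and receives combination therapy in Cycle 2. Section 7.2.4.1.1 requires olaratumab to be stopped immediately and permanently after a Grade 3 or 4 infusion reaction. Sections 7.2.2 and 7.2.4 take a patient whose olaratumab is stopped for toxicity off the study.

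**The concern.** A site treating a child who has had a life-threatening toxicity should find one answer to whether, and how often, the drug may be given again. Here there are two. The DLT rule with the dose ladder leaves a further reduced dose open after a second Grade 4 event; the Grade 4 row of Table JGDN.7.5 closes it. The only sentence that divides cases between the rules turns on whether the event is dose-limiting, and that test does not separate Grade 4 nonhematologic events.

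The Section 6.2 sentence raises the same kind of problem more directly. Read literally, it continues olaratumab in a child for whom another section says the drug must be stopped for good. What is at stake is individual patient safety, not the trial's estimates.

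**Working it through.** There is no planned figure to reproduce. The check sets the rules side by side and then sizes the exposure.

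**Step 1. Is any olaratumab-related Grade 4 nonhematologic event not dose-limiting?**

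- *Grade.* Protocol 7.2.3.1 sets the threshold at Grade 3 or higher "nonhematologic toxicity. Exceptions will be made for" a list in which every item is Grade 3. Grade 4 has no exception. The SAP prints a threshold above Grade 3, which still includes Grade 4.
- *Relatedness.* A DLT needs only a possible relation to study drug. Under Protocol 8.1.2, possibly related "AEs and SAEs will be defined as related to study drug".
- *Timing.*

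| Part | Cycle | Status | Source |
|---|---|---|---|
| A, B | 1 | DLT | Protocol 7.2.3.1 |
| A, B | 2 | DLT | Protocol 7.2.3.2; SAP 5.3.1 |
| A, B | 3 onward | DLT-equivalent | Protocol 7.2.4 |
| C | 1 | DLT | Protocol 7.2.3.1 and 7.2.3.2 |
| C | 2 onward | DLT-equivalent | Protocol 7.2.4 |

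For Cycle 2 of Parts A and B, the evidence is that Protocol 7.2.3.2 applies the DLT rate "in the first cycle (Parts A and B Cycle 2, or Part C Cycle 1) of any of the chemotherapy arms" and that the SAP states "Dose-limiting toxicity is defined as an AE during Cycle 1 (Cycle 2 for combination treatment" for these parts. Only a literal reading of the 21-day window in 7.2.3.1 would leave that cycle out.

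No cycle remains. For these events the set that the first pointer sends to 7.2.4.1.3 is empty.

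**Step 2. Does Table JGDN.7.5 still apply?** Yes. The later list in 7.2.4 names 7.2.4.1.3 without the limit, and neither that section nor the Grade 4 row excludes DLTs. The same event therefore falls under both rules.

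**Step 3. Where do the outcomes differ?**

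| Start dose | Event | 7.2.4 with Table JGDN.7.3 | Table JGDN.7.5, Grade 4 row |
|---|---|---|---|
| 20 mg/kg | First | 15 mg/kg | 15 mg/kg; consider stopping for good |
| 20 mg/kg | Recurrence | 10 mg/kg available | Stop |
| 15 mg/kg | First | 10 mg/kg | 10 mg/kg; consider stopping for good |
| 15 mg/kg | Recurrence | Stop | Stop |

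The recurrence conflict is confined to a 20 mg/kg start.

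**Step 4. Infusion reactions in Part B.** A related Grade 3 or 4 infusion reaction is a nonhematologic event of Grade 3 or higher, so in Cycle 1 it is a DLT. Section 6.2 then gives 15 mg/kg plus chemotherapy; 7.2.4.1.1 gives permanent discontinuation. The overlap is not remote: Section 7.2.1 reports that Grade 3/4 reactions have so far occurred only in the first cycle.

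**Step 5. Size.** The documents give no pediatric rate. The nearest source is the olaratumab arm in Table JGDN.5.2 (64 adults, 15 mg/kg with doxorubicin, common events only).

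- Grade 4 or higher nonhematologic events, leaving out infusion reactions (own rule) and febrile neutropenia (own row in Table JGDN.7.4): 0/64, exact 95% CI 0 to 5.6%.
- Counting the one febrile neutropenia: 1/64 = 1.6%, CI 0.04% to 8.4%.
- First events if these rates held in 45 children: 45 × 0 = 0 to 45 × 1/64 = 0.70. At the upper limits: 45 × 5.6% = 2.5 and 45 × 8.4% = 3.8.
- Recurrence after restart, assumed at 10% to 50%: 0.70 × 0.1 = 0.07 to 0.70 × 0.5 = 0.35 children, or 0 if the first-event rate is 0. The extreme is 3.78 × 0.5 = 1.9.
- Infusion reactions of Grade 4 or higher: 2/64 = 3.1%, with none at Grade 3. For a Part B of 10 (Protocol) or 12 (SAP): 10 × 2/64 = 0.31 or 12 × 2/64 = 0.38 children.

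**The case against.** The strongest reply is that a sensible reader can reconcile the rules. The DLT sentence permits resumption; Table JGDN.7.5 forbids it after recurrence; a site that stops breaches neither. Table JGDN.7.3 lists available dose steps and does not itself authorise 10 mg/kg after a second Grade 4 event. The subsection on infusion reactions plainly overrides the DLT sentence although the first pointer does not name it, and by the same logic Table JGDN.7.5 would override it too. Both routes also involve the sponsor's physician, and Section 6.3.1 removes patients for unacceptable toxicity in any case.

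Much of this stands. It shows that the protective reading is available and probably intended. It does not show that the protocol states it. Table JGDN.7.5 is labelled general guidance, so a site could equally treat the DLT sentence as the more specific rule. Consultation leaves the decision open where the table makes it mandatory. The reconciliation also does not reach Section 6.2, which says what will happen and carries no exception.

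A reader might go further and infer that the Grade 4 row can never be reached, because the first pointer is empty for Grade 4. The documents do not support that: the second reference in 7.2.4 carries no such limit, and the row covers any patient with the event.

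A reader might also see a conflict in the recovery thresholds: baseline in the DLT sentence, Grade 1 or less or baseline in Table JGDN.7.5, and "Grade <2 or equivalent severity to baseline" for starting a cycle. The cycle-start list is a minimum, and baseline after a DLT is a stricter added condition; both can be met. Forcing one threshold would be a preference, and would delay children with residual Grade 1 toxicity.

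**Conclusion.** The point holds as an overlap of two rules without stated precedence, plus a direct contradiction between Section 6.2 and Section 7.2.4.1.1. On recurrence the overlap changes the outcome only for a 20 mg/kg start. The 45 places in Parts B and C are the number exposed to the rule, not the number affected. Few or no children are likely to meet either situation.

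The size rests on adult data at a lower dose, with one chemotherapy partner and common events only, and on an assumed recurrence range for which the documents give no basis. The figure of 1.9 combines an upper confidence limit with the top of that range. The adult data cannot exclude a higher risk in children at 20 mg/kg. DLT counts and the recommended dose are unaffected. The case for correcting the text is the gravity of the event and the small cost, not frequency.

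**What to change.** 1. Add one statement to Protocol 7.2.4: *For Grade 4 nonhematologic toxicity related to olaratumab, the Grade 4 row of Table JGDN.7.5 (consider permanent discontinuation; discontinue olaratumab if Grade 4 recurs) also applies to, and takes precedence for, DLTs and DLT-equivalents. Section 7.2.4.1.1 governs infusion-related reactions.*
2. In the Part B text of Section 6.2, after the reduction to 15 mg/kg following a Cycle 1 DLT, add: *unless Section 7.2.4.1.1 or Table JGDN.7.5 requires discontinuation.*

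Leave the recovery thresholds and the cycle-start criteria as they are.

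The cost is a few lines of protocol wording, with no extra data, visits or patients. The downside is that a few children would stop olaratumab, and so leave the study, after a second Grade 4 event.
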